#### 7 Sample Size

#### Safety:

This is a one proportion study powered at 80% and a one-sided 2.5% significance. The published literature supports a Major AE rate of 12%. As there are no approved devices in the space, a non-inferiority margin of 10% was selected and is supported by the Renata Physician advisors.

Based on published data (Holzer) the incidence of device or procedure-related SAEs on the current treatment procedure is 10% in patients > 1 year of age and 14% in patients  $\leq$ 1 year of age; therefore, a blended rate of 12% will be used. Clinically, it is generally believed that incidences of SAEs less than 22% are clinically acceptable. Therefore, we are adopting a performance goal of 22% for the SAE rate.

Based on the clinically acceptable rate of 22%, the hypothesis would then be written as the following:

Null Hypothesis (H0): Incidence of device or procedure-related SAE  $\geq$  22% Alternative Hypothesis (HA): Incidence of device or procedure-related SAE <22% One-Sided (H0: P  $\geq$  P0 vs. H1: P < P0)

Assuming an SAE rate of 4% (Boe), 30 subjects will provide 80% power to meet the performance goal and reject the null hypothesis at a 2.5% one-sided significance level. The sample size calculation was based on the normal approximation to the binomial distribution.

#### Efficacy:

This is a one proportion study powered at 80% and a one-sided 2.5% significance. The published literature supports a procedural effectiveness rate of 87%. As there are no approved devices in the space, a non-inferiority margin of 10% was selected and is supported by the Renata Physician advisors.

Based on published data (Stanfill) the incidence of angiographic success during implantation is 87%. Clinically, it is generally believed that a procedural success rate greater than 77% is clinically acceptable. Therefore, we are adopting a performance goal of 77% for procedural effectiveness.

Based on the clinically acceptable rate of 77%, the hypothesis would then be written as the following:

Null Hypothesis (H0): Incidence of clinical success  $\leq$ 77%. Alternative Hypothesis (HA): Incidence of clinical success >77%. One-Sided (H0: P  $\leq$  P0 vs. H1: P > P0)

Assuming a clinical success rate of 97% (Boe), 24 subjects will provide 80% power to meet the performance goal and reject the null hypothesis at a 2.5% one-sided significance level. The sample size calculation was based on the normal approximation to the binomial distribution.

Co-Primary Endpoint Power Calculation:

For the study to successfully pass, all both Safety & Efficacy Primary Endpoints must reject their null hypothesizes concurrently, using the appropriate one-sided significance level for each endpoint (2.5% and 2.5% respectively); therefore, power calculations were performed for each hypothesis statement, based on the normal approximation to the binomial distribution, and combined using the Inclusion-Exclusion Rule (shown below), assuming the two endpoints are independent, to determine the power of the study at each sample size.

$$\begin{split} P(A \cup B) &= P(A) + P(B) - P(AB) \\ & Where: \\ P(A) &= \beta_{Efficacy} \\ P(B) &= \beta_{Safety} \\ P(AB) &= \beta_{Efficacy} \ x \ \beta_{Safety} \\ P(A \cup B) &= \beta_{Efficacy} \ \& Safety \\ Study \ Power &= 1 - \beta_{Efficacy} \ \& Safety \\ \end{split}$$

Using the assumptions above, analysis shows a minimum of 36 subjects will provide 90% power to meet both the primary efficacy and safety performance goals. To account for approximately 15% attrition rate, a maximum of 42 United States subjects (42=36(100%+15%)) will be allowed to be implanted, prior to further authorization.

Sample	Safety	Efficacy	Total
Size	Power	Power	Power
20	0.49	0.66	0.32
21	0.53	0.70	0.37
22	0.57	0.75	0.42
23	0.60	0.78	0.47
24	0.64	0.82	0.52
25	0.67	0.85	0.57
26	0.71	0.87	0.62
27	0.74	0.90	0.66
28	0.76	0.91	0.70
29	0.79	0.93	0.73
30	0.81	0.94	0.77
31	0.83	0.95	0.80
32	0.85	0.96	0.82
33	0.87	0.97	0.85
34	0.89	0.98	0.87
35	0.90	0.98	0.89
36	0.91	0.99	0.90
37	0.93	0.99	0.92
38	0.94	0.99	0.93
39	0.94	0.99	0.94
40	0.95	1.00	0.95

GROWTH: A Multicenter Pivotal Study of Neonatal, Infant, and Young Child Vascular Stenoses Studying the Renata Minima Stent DOC-0008 Rev. A 01/24/2024 Page 13 of 19

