# **10 Efficacy Analyses**

### **10.1 Primary Efficacy Analysis**

The primary efficacy endpoint will be assessed as the rate of clinical success, with the performance goal defined as a clinical success rate of greater than 77%.

Clinical success is defined as:

- Stenosis relief, defined by stent outer diameter  $\geq$  75% of the surrounding vessel immediately after deployment.
- Freedom from open surgical intervention required to treat Minima Stent disfunction through 6 months.
- Maintenance of stented vessel diameter ≥ 50% of post-implant diameter at 6 months; as measured using CT angiography and/or angiography.

The AI patient population will be used to test the study hypothesis. The Clopper-Pearson method will be used to calculate the two-sided 95% confidence limits. If the lower limit of the resulting confidence interval exceeds 77%, then the null hypothesis will be rejected in favor of the alternative. This study hypothesis will be tested without imputation of missing data; however, additional sensitivity analyses will be performed to evaluate the effect of missing data on the study conclusions.

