# 11 Safety Analyses

#### **11.1 Primary Safety Analysis**

The primary safety endpoint will be assessed as the percentage of cases with freedom from procedure- or device-related SAEs resulting in an event listed below, with the performance goal defined as greater than 78% of cases:

- o Death
- o Cardiac arrest and/or emergency ECMO cannulation
- o Stroke
- o Limb loss
- Vessel dissection of target lesion
- Device thrombosis/occlusion
- Cardiac perforation requiring percutaneous or open surgical intervention
- Persistent cardiac arrhythmia requiring a pacemaker

The AT patient population will be used to test this hypothesis. The Clopper-Pearson method will be used to calculate the two-sided 95% confidence limits. If the lower limit of the resulting confidence interval exceeds 78%, then the null hypothesis will be rejected in favor of the alternative. The study hypothesis will be tested without imputation of missing data; however, additional sensitivity analyses will be performed to evaluate the effect of missing data on the study conclusions.

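### The stated 90% joint power at 36 subjects (and 80% safety power at 30) comes from a normal approximation; the exact Clopper-Pearson rule that will be used gives about 81% (and 66%)

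*SAP*

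**What the plan says.** SAP Section 7 sizes each co-primary endpoint separately and then jointly.

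- **Safety:** for a null SAE rate of 22% and an assumed rate of 4%, "30 subjects will provide 80% power to meet the performance goal and reject the null hypothesis at a 2.5% one-sided significance level".
- **Method:** "The sample size calculation was based on the normal approximation to the binomial distribution". The same basis is stated for efficacy (null 77%, assumed 97%, 24 subjects for 80% power) and for the joint calculation.
- **Joint power:** the two powers are combined assuming independence, and "analysis shows a minimum of 36 subjects will provide 90% power to meet both the primary efficacy and safety performance goals". The table row for 36 reads 0.91 (safety), 0.99 (efficacy) and 0.90 (total).
- **Attrition:** an allowance of about 15% raises 36 to a maximum of 42 US subjects. Section 6.1 gives the study size as 36 to 42 patients.

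The analysis sections specify a different procedure. In Section 10.1, "The Clopper-Pearson method will be used to calculate the two-sided 95% confidence limits", and the efficacy null is rejected if the lower limit is above 77%. Section 11.1 uses the same interval for safety: "If the lower limit of the resulting confidence interval exceeds 78%, then the null hypothesis will be rejected in favor of the alternative". Neither document gives a power calculated for that rule.

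**The concern.** A power figure is informative only if it is the probability that the planned test succeeds. Here the power was computed for a large-sample z-test and the decision will be made with an exact binomial limit. At 36 subjects the plan expects 36 × 0.04 = 1.4 safety events and 36 × 0.03 = 1.1 efficacy failures. With counts that small, the outcome depends on whether two or three failures are allowed, and a smooth approximation cannot show that.

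The 90% figure is the plan's only quantitative support for 36 as the minimum size of a single-arm pivotal study in which both endpoints must pass. If it is wrong, the sponsor is accepting a higher risk of failure than the document states, and the table gives no sign of it.

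**Working it through.** **Inputs, all from SAP Sections 7, 10.1 and 11.1.** Safety, as freedom from events: p0 = 0.78, p1 = 0.96. Efficacy: p0 = 0.77, p1 = 0.97. One-sided 2.5% for each endpoint, both must reject, endpoints independent.

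**Step 1. Reproduce the stated figures.** The table follows from the normal approximation with the null variance in the critical value:

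power = Φ( [ (p1 − p0)√n − 1.96 √(p0(1 − p0)) ] / √(p1(1 − p1)) )

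- Safety, n = 36: Φ( [0.18 × 6 − 1.96 √(0.78 × 0.22)] / √(0.96 × 0.04) ) = Φ(1.368) = 0.914
- Efficacy, n = 36: Φ( [0.20 × 6 − 1.96 √(0.77 × 0.23)] / √(0.97 × 0.03) ) = Φ(2.199) = 0.986
- Joint: 0.914 × 0.986 = 0.902
- Safety, n = 30: Φ(0.888) = 0.813
- Efficacy, n = 24: 0.818

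These match the table (0.91, 0.99, 0.90, 0.81, 0.82), so the source of the stated power is clear.

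**Step 2. Find the pass counts under the planned rule.** The pass count is the smallest number of successes whose two-sided 95% Clopper-Pearson lower limit exceeds the goal.

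| Endpoint | n | Passes at (lower limit) | One fewer (lower limit) |
|---|---|---|---|
| Safety, goal 0.78 | 36 | 34/36 (0.813) | 33/36 (0.775), fails |
| Efficacy, goal 0.77 | 36 | 33/36 (0.775) | 32/36 (0.739), fails |
| Safety, goal 0.78 | 30 | 29/30 (0.828) | 28/30 (0.779), fails |
| Efficacy, goal 0.77 | 24 | 23/24 (0.789) | 22/24 (0.730), fails |

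**Step 3. Exact binomial power at those counts.**

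- Safety, n = 36, at most 2 events at 4%: 0.2300 + 0.3450 + 0.2516 = 0.827
- Efficacy, n = 36, at most 3 failures at 3%: 0.3340 + 0.3719 + 0.2013 + 0.0706 = 0.978
- Joint, n = 36: 0.8266 × 0.9778 = 0.808
- Safety, n = 30, at most 1 event: 0.2939 + 0.3673 = 0.661
- Efficacy, n = 24, at most 1 failure: 0.839, so no shortfall there

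**Step 4. Dependence between endpoints.** Without independence, joint power at 36 lies between 0.8266 + 0.9778 − 1 = 0.804 and the smaller of the two powers, 0.827. The result of about 81% does not depend on the independence assumption.

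**Step 5. Other sizes, same n for both endpoints.**

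| n | Joint power, SAP table | Joint power, exact |
|---|---|---|
| 30 | 0.77 | 0.62 |
| 31 | 0.80 | 0.82 |
| 34 | 0.87 | 0.78 |
| 35 | 0.89 | 0.76 |
| 36 | 0.90 | 0.81 |
| 37 | 0.92 | 0.92 |
| 38 | 0.93 | 0.91 |
| 39 | 0.94 | 0.90 |
| 40 | 0.95 | 0.896 |
| 41 | not given | 0.888 |
| 42 | not given | 0.906 |

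Exact power is saw-toothed. It falls from 0.82 at 31 to 0.76 at 35, while the SAP table rises from 0.80 to 0.89. It then gains 11 points between 36 and 37, because safety may have three events from 37 onwards.

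**Step 6. Attrition.** A 15% loss from 42 leaves 42 × 0.85 = 35.7 subjects. Safety is tested in the All Treated population and efficacy in the Attempted Implant population, and the SAP does not say how loss would fall on each. As assumed scenarios:

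- 42 for safety and 36 for efficacy: 0.914 × 0.978 = 0.893
- 42 for safety and 35 for efficacy: 0.914 × 0.913 = 0.834
- 35 for both (worst of the three): 0.764

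**The case against.** The SAP states openly that it used the normal approximation, and its table is right for that method; the fault is a mismatch between method and test, not a slip in calculation. The mismatch does not always flatter the plan: at 31 subjects, and for efficacy at 24, exact power is above the stated value. The size of 36 is also an unlucky point, since 33/36 only just misses the 78% safety goal. At 37 to 42 evaluable subjects, exact joint power is 0.89 to 0.92. Each endpoint still exceeds its own 80% target at 36. The 30-subject figure is only a step towards the final size. Clopper-Pearson holds the one-sided error at or below 2.5%, so a positive result would remain valid and the added risk is the sponsor's.

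All of this is correct, and it limits the consequence. It does not rescue the statement. Disclosing an approximation does not make its result true of another test. The SAP makes its 90% claim at 36, which Section 6.1 treats as an operative size, and at 36 the claim is out by 9 points. That 36 is a low point of the saw-tooth is exactly what the table should show. Full enrolment of 42 does not guarantee more than 36 evaluable subjects, because the SAP's own 15% allowance leaves about 36.

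**Conclusion.** The concern holds. For the test the SAP specifies, and under its own assumptions of 96% freedom from events and 97% success, 36 subjects give about 81% joint power rather than 90%. The chance of missing a co-primary goal is 1 − 0.808 = 0.19, about twice the stated 10%. Safety power at 30 subjects is 66%, not 80%.

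Safety causes most of the shortfall at 36: it loses about 9 points (0.914 to 0.827), while efficacy loses about 1 (0.986 to 0.978). The conclusion applies to the stated minimum. With 42 evaluable for both endpoints, joint power is 0.906. The figure of 0.76 applies only if both endpoints are left with 35. The validity of the test is not in question.

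**What to change.** 1. Recompute Section 7 and every row of the power table with the exact binomial rule of Sections 10.1 and 11.1, extended to 42.
2. Restate the headline figures: about 81% joint power at 36 evaluable subjects, and 66% safety power at 30.
3. Print the pass counts, for example at least 34/36 event-free and at least 33/36 clinical successes.
4. If a 90% figure is to be kept, it can be quoted at 37 evaluable subjects (0.918), within the cap of 42. It should stand beside the full table, because exact joint power drops to 0.896 at 40 and 0.888 at 41; 37 is not a size from which 90% is maintained.
5. State how many subjects are expected to be evaluable for each endpoint after attrition, and give the power for that split.

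The power statement should be changed, not the test. A z-test using the null variance would accept 33/36 for safety, and its exact one-sided error there is 0.029, above the planned 2.5%.

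The cost is revised wording, a recomputed table and a less favourable stated figure. Endpoints, performance goals, decision rules and the cap of 42 do not change.

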# 8 General Analysis Considerations

#### 8.1 Timing of Analyses

The first analysis will be performed when a minimum of 10 subjects have completed the 6 month visit.

Primary analysis and submission of available data will be completed after all patients have completed their 6 month follow-up visits.

Subsequent analysis will be completed annually through 5 years.

#### 8.2 Analysis Populations

- 8.2.1 The All Treated (AT) population is defined as all subjects who signed informed consent, meet eligibility criteria and for whom a procedure was begun (defined as the initiation of vascular access).
- 8.2.2 The Attempted Implant (AI) population is defined as all AT subjects who continued to meet the eligibility criteria and had an attempted implant of the Minima stent. A subject is considered to have an attempted implant at the time in which the Minima Stent System is inserted into the subject.

#### 8.3 Interim Analyses

There are no plans for an interim analysis at this time.

# 9 Summary of Study Data

All continuous variables will be summarized using the following descriptive statistics: n (non-missing sample size), mean, standard deviation, median, maximum and minimum. The frequency and percentages (based on the non-missing sample size) of observed levels will be reported for all categorical measures. All summary tables will be structured with a column for treatment and will be annotated with the total population size relevant to that table, including any missing observations.

Only deviations from the general overview will be noted in the subsequent sub-sections within section 9.

#### 9.1 Subject Disposition

The number of patients completing each visit from the schedule of assessments will be reported along with the reason for loss (screen failure, death, loss to follow-up, etc).

The summary statistics will be produced in accordance with section 9.

#### 9.2 **Protocol Deviations**

All protocol deviations will be summarized.

If a stent is removed surgically during another procedure (which is unrelated to a Minima Stent malfunction/failure) the data collected prior to stent removal will be included within analysis. After stent removal, no additional data related to the stent will be collected and the sample size will be reduced accordingly in any applicable calculations.

If a patient is found to not meet eligibility criteria per the protocol inclusion/exclusion criteria, they will not be treated under the protocol and the appropriate regulatory filing must be completed prior to treating the patient outside of the protocol. All patients treated off protocol will not be included in analysis.

The summary statistics will be produced in accordance with section 9.

#### 9.3 Demographic and Baseline Variables

The summary statistics will be produced in accordance with section 9.

#### 9.4 Concurrent Illnesses and Medical Conditions

The summary statistics will be produced in accordance with section 9.

# **10 Efficacy Analyses**

### **10.1 Primary Efficacy Analysis**

The primary efficacy endpoint will be assessed as the rate of clinical success, with the performance goal defined as a clinical success rate of greater than 77%.

Clinical success is defined as:

- Stenosis relief, defined by stent outer diameter  $\geq$  75% of the surrounding vessel immediately after deployment.
- Freedom from open surgical intervention required to treat Minima Stent disfunction through 6 months.
- Maintenance of stented vessel diameter ≥ 50% of post-implant diameter at 6 months; as measured using CT angiography and/or angiography.

The AI patient population will be used to test the study hypothesis. The Clopper-Pearson method will be used to calculate the two-sided 95% confidence limits. If the lower limit of the resulting confidence interval exceeds 77%, then the null hypothesis will be rejected in favor of the alternative. This study hypothesis will be tested without imputation of missing data; however, additional sensitivity analyses will be performed to evaluate the effect of missing data on the study conclusions.

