#### **Missed window**

For missed data collection, confidence intervals, standard deviations and other calculations dependent on sample size will be calculated using the reduced sample size, unless noted otherwise in the resolution of the protocol deviation.

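### The SAP does not say how a child with no stent deployed, or one who dies before the 6-month image, counts in the primary efficacy test, and its missing-data rules allow such children to leave the denominator

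*SAP*

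**What the plan says.** **Population.** SAP 10.1 runs the primary efficacy test in the AI population. SAP 8.2.2 defines entry by insertion, not deployment: "A subject is considered to have an attempted implant at the time in which the Minima Stent System is inserted into the subject".

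**Endpoint.** Clinical success (SAP 5.2 and 10.1) has three parts:
1. a stent diameter of at least 75% of the surrounding vessel, taken just after deployment;
2. no open surgery for stent dysfunction through 6 months;
3. a 6-month diameter, by CT or catheter angiography, of at least 50% of the post-implant value.

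**Decision rule.** The two-sided 95% Clopper-Pearson lower limit must exceed 77%.

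**Unmeasured values.**
- SAP 10.1: "This study hypothesis will be tested without imputation of missing data". SAP 13 repeats this for both primary endpoints.
- SAP 6.3, under the missed-window heading: "confidence intervals, standard deviations and other calculations dependent on sample size will be calculated using the reduced sample size", unless the resolution of a protocol deviation says otherwise.
- SAP 9 bases percentages on the non-missing sample size.
- SAP 9.2 reduces the sample size after surgical stent removal unrelated to stent malfunction.
- SAP 9.1 lists death among the reasons for loss in the disposition summary.
- SAP 13 makes missing-as-failure a sensitivity analysis. If the conclusion is not upheld, a tipping-point analysis and multiple imputation follow.

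**The concern.** Two kinds of AI child cannot have all the measurements that the composite needs. A child in whom the system was inserted but no stent deployed has no post-deployment diameter. A child who dies before the 6-month image has no 6-month diameter. Neither reached 6-month clinical success, yet the SAP does not say that either is a failure. The only rules that reach an unmeasured value shrink the denominator.

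The clearest gap is a death after a technically good implant. That child has passed part 1, had no surgery for stent dysfunction, and has no value for part 3. Applied as written, the child leaves the test. If the worst-case run then fails, multiple imputation could score the same child a success, although the outcome is known.

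At stake is the pass/fail result of a single-arm pivotal study in which few failures are tolerated. Two analysts could follow the SAP and reach different conclusions from the same data.

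**Working it through.** **1. Inputs.** From SAP 7: performance goal 0.77, assumed success 0.97, one-sided 2.5%; 36 subjects for 90% joint power, maximum 42. From SAP 10.1: the Clopper-Pearson rule. The number or share of unmeasurable children is not in the documents, so it is assumed and shown as a range.

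**2. The plan's own figure.** SAP 7 says that "24 subjects will provide 80% power to meet the performance goal". With the normal approximation, power = Φ[(|p1 − p0| − 1.96·√(p0(1 − p0)/n)) / √(p1(1 − p1)/n)]. For n = 24:
- √(0.77 × 0.23/24) = 0.0859 and √(0.97 × 0.03/24) = 0.0348
- (0.20 − 1.96 × 0.0859)/0.0348 = 0.91, so power is 0.818 (table: 0.82)

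At n = 36 the formula gives efficacy 0.986, safety 0.914 and joint 0.902 (table: 0.99, 0.91, 0.90). The stated figures reproduce. The issue is the denominator, not the sample size formula.

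**3. Failures allowed if every AI child stays in.** The lower limit is the 0.025 quantile of Beta(x, n − x + 1). At n = 42, 38 successes are needed (lower limit 77.4%), so 4 non-successes are allowed. At n = 36, 33 are needed (77.5%), so 3 are allowed.

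**4. Same successes, two denominators.** Each row takes the smallest passing count after the assumed number of children is dropped.

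| AI children | Dropped (assumed) | Reduced denominator | All AI children |
|---|---|---|---|
| 42 | 1 | 38/41, 80.1%, pass | 38/42, 77.4%, pass |
| 42 | 2 | 37/40, 79.6%, pass | 37/42, 74.4%, fail |
| 42 | 6 | 33/36, 77.5%, pass | 33/42, 63.2%, fail |
| 36 | 2 | 32/34, 80.3%, pass | 32/36, 73.9%, fail |

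Percentages are lower limits. Six is 42 − 36, the whole attrition allowance in SAP 7, and so is an extreme case.

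**5. Type I error.** Suppose true success over all AI children is 0.77 and a share q, all non-successes, is dropped. Success among the rest is then 0.77/(1 − q). The error is Σₘ Bin(m; N, q) × P(X ≥ t(N − m)), where X is binomial with N − m children and probability 0.77/(1 − q), and t(n) is the smallest passing count for n.

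| q (assumed) | 0.77/(1 − q) | N = 42 | N = 36 |
|---|---|---|---|
| 0 | 0.770 | 2.2% | 2.1% |
| 2% | 0.786 | 2.5% | 2.3% |
| 5% | 0.811 | 4.7% | 3.8% |
| 10% | 0.856 | 17.1% | 13.5% |

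At q = 2% the error is still at the nominal 2.5%. It rises materially only from about 5%.

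**The case against.** A reader might infer that the SAP orders deaths and failed deployments to be excluded, so that the test becomes a rate among children who received a stent, survived and were imaged. The documents do not support that. No section says that these children are missing data. The reduced-sample rule in SAP 6.3 concerns missed data collection and mentions neither event. SAP 9.1 is a disposition summary whose list also includes screen failure, so it does not define endpoint scoring.

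Other points on that side also stand:
- Starting the AI population at insertion suggests an intent to keep failed attempts in, and a child with no stent deployed is naturally read as failing stenosis relief. The SAP does not say so, but this half of the gap is the weaker one.
- The composite requires all three parts, so a child who failed part 1 or 2 is a known failure without a 6-month image.
- The Month 6 analysis window runs from day 136 to day 270, so a child imaged in that window who dies later may be evaluable.
- Procedure- or device-related deaths count in the co-primary safety endpoint on the wider All Treated population, and both endpoints must pass.
- SAP 13 would display the effect through the worst-case and tipping-point analyses.
- The flip depends on the counts. With one measured failure among 42, dropping up to three children does not change the decision, because 38/42 still passes.
- Whether an unrelated death is a device failure is an estimand choice on which statisticians can differ.

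These points narrow the concern without removing it. None classifies a death after a good implant for efficacy, and the SAP does not say that failing the worst-case run changes the primary conclusion.

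**Conclusion.** The gap is real and should be closed before the primary analysis. It is an unclassified outcome, not an instruction to exclude. The SAP permits children who die before the 6-month image, and on a less natural reading those with no stent deployed, to leave the primary efficacy denominator.

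Two such children can turn a fail into a pass at 42 or at 36 AI children; one cannot at the threshold for 42. Type I error is materially above nominal only if about 5% or more of AI children are dropped. These sizes rest on assumed counts and shares. They also treat every dropped child as a non-success, which for unrelated deaths depends on the estimand chosen. Only the synopsis of the protocol was available, so a definition elsewhere in the full protocol cannot be ruled out.

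This is a should-fix point: the wording is open at a place that can decide the result, but the natural reading, the safety endpoint and SAP 13 limit the exposure.

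**What to change.** In SAP 10.1 and 13:

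1. State that, in the primary test, these are observed failures and are not eligible for multiple imputation: an attempt without a deployed stent; failure of part 1 or part 2; and a procedure- or device-related death before an in-window 6-month measurement.
2. Limit missing to implanted children without an in-window image who have not already failed. The no-imputation rule and the SAP 13 sensitivity analyses then apply to them alone.
3. State in advance how unrelated deaths and unrelated surgical stent removal are handled, and reconcile this with SAP 6.3, 9 and 9.2.
4. Add a supportive analysis that keeps all AI children in the denominator and counts unrelated deaths as failures.

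The change is to SAP wording only and needs no new data. The cost is a less favourable rate, slight if such cases are rare. If 97% success holds among the other children and a share q counts as failures, exact efficacy power at 42 is 99.2% (q = 0), 94.5% (2%) and 76.9% (5%); at 36 it is 97.8%, 90.0% and 68.8%. The q values are again assumptions.
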